### **Aim 3: I-HoME pilot RCT**

For Aim 3, 100 CGs will be recruited from VNS Health hospice teams. The intervention will be randomized by nurse. Therefore, CGs of certain nurses will receive the I-HoME intervention (n=50) for up to six weeks while others will be recruited to receive standard home hospice care (n=50). Feasibility and potential efficacy measures will be administered at baseline and after each visit/weekly (timeline may change based on results obtained from Aim 2). Baseline measures will be collected during the in-home visit or via phone call by the research team and subsequent measures will be collected via phone call or electronic survey.

**Intervention.** CGs randomized to the intervention group will have access to live synchronous video visits with a research nurse interventionist on a scheduled (weekly) and as-needed basis (hours will be dependent on funding). The study team will either make an in-home visit or conduct a phone call with the CG (based on CG preference) at the start of the study to obtain consent and train the CG on the I-HoME intervention. This group will be educated about I-HoME and learn how to use the tablet to access videos and communicate with the interventionist. Participants will also be given a laminated user guide/help card and have access to technical assistance if hardware or software concerns arise or if an adverse event occurs. Software by Doxy.me will be used to conduct HIPAA compliant synchronous video visits. Participants in this study will continue to receive standard home hospice care in addition to the I-HoME intervention. Phone visits will be conducted if video visits are unable to be done due to hardware or software issues.

**Standard Care Control.** Participants in the standard care control group will receive home hospice services as usual. They will also receive a tablet with hospice resources. These participants will complete the same measures as participants in the intervention condition on the same timeline using identical assessment procedures.

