**Measurements.** All participants will be assessed on the measures listed in Table 2 (see **Appendix B** for more details). Measures will be administered at baseline and in weeks 1, 2, 3, 4, 5 and 6. Validated surveys will be administered via phone by a research assistant. Post-visit measures for caregivers will be collected during each interview, and additional measures will be collected during the final interview. Participants will be compensated \$50 for an initial baseline survey followed by \$25 (by ClinCard) each time they complete a within study phone call/electronic survey. Post-intervention measures for patients will be collected from their medical chart in both groups. For the intervention group, the collection will start from study enrollment to 4 weeks after the final I-HoME intervention visit or the date of program end (which ever one is earlier). For the control group, the collection will start from study enrollment to 11 weeks after enrollment.

Table 2.

Baseline measures		Post-intervention measures	
Patient (from medical chart)	Caregiver	Caregiver	Patient
Age	Age	Burden	Hospice discharge reason
Gender	Gender	Depression	Use of non-home hospice services (inpatient care, respite care)
Race/ethnicity	Race/ethnicity	Anxiety	Number of nursing visits
DNI/DNR status	Religion	Software issues	Number of social work visits
Medications	Education	Hardware issues	Number of chaplain visits
Comorbidities	Relationship to patient	Patient symptoms	
Hospice diagnosis	Hours providing care to patient	CaSES	
	Number of CGs caring for the patient	Caregiver (Final Interview)	
	Occupation	CG Satisfaction	
	Income	Feasibility questionnaire	

### Addition of patient participants for Aim 3

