For post-test power assessment, the selection of 100 patient–CG dyads is based on power calculations with an all-cause attrition rate on not filling out post-test assessments of 10%, leaving 90 dyads. For post-test comparisons of post-intervention measures under a two-tailed hypothesis, we will have 80% power to detect a group-by-time interaction with an effect size of  $d=0.66$ , which is regarded as a medium-large effect size. A data collection protocol whereby data are collected at baseline and in weeks 1, 2, 3, 4, 5, and 6 would correspond to 7 measurements for subjects who complete the 6-week intervention/pilot test. To conduct a power-analysis we conducted a simulation to model attrition directly. We assumed everyone would have at least 1 measurement after hospice discharge, including patients who died during week 1 of the intervention. The mortality rate modeled using samples drawn from data on 1,000 home hospice patients was 35% at four weeks, 62% at eight weeks, and 72% at twelve weeks. This means we would have 7 measurements on approximately 28% of the data.

Our power to detect effects will depend largely, on how quickly the intervention is successful. With two time points for each subject we will have 80% power to detect an effect size of  $d=0.57$  on any outcome, which is considered a moderate effect. If it takes the full 7 time points for the full effect of the intervention to be realized our power will be reduced and we will require a large effect ( $d=0.8$ ) to obtain 80% power. A 25% reduction in burden reported by family CGs corresponds to an effect size of 0.71. Under a two-tailed hypothesis test, if the intervention is successful by week 1, we would have 94% power to detect an effect of this size. We would have 70% power for a two-tailed hypothesis test across 7 time points.

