#### Brief Description of Project Design

For Aim 1, ten home hospice providers (e.g., nurses, nurse practitioners, physicians) along with ten home hospice patients and their ten family CGs will be interviewed individually and recruited from the Visiting Nurse Service of New York (VNSNY) to provide feedback on the I-HoME intervention.

For Aim 2, ten patient/caregiver dyads will be recruited for the i-HoME intervention which will be delivered for up to a 6-week period. Based on the data gathered from the single armed pilot study, modifications will be made to the data collection protocols and intervention prior to moving on and conducting the pilot RCT.

For Aim 3, 100 patient and CG dyads will be recruited from VNSNY and randomly assigned, by hospice team, to either I-HoME (n=50) or to standard home hospice care (n=50) for twelve weeks. Feasibility and potential efficacy measures will be administered at baseline and in weeks 1, 2, 3, 4, 5 and 6. Post-intervention measures will be collected at the end of the intervention 4 weeks after a patient's death.

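### The 28% said to have all seven measurements is week-12 survival, but the seventh measurement is at week 6, when the plan's own mortality leaves 38% to 65% alive

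*Combined protocol and SAP*

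**What the plan says.** All of the power reasoning is in the combined protocol and SAP, under Brief overview of analytic methods.

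- **Schedule.** Data "collected at baseline and in weeks 1, 2, 3, 4, 5, and 6 would correspond to 7 measurements" for someone who completes the six weeks. The Aim 3 section agrees: "Measures will be administered at baseline and in weeks 1, 2, 3, 4, 5 and 6", with caregivers of certain nurses who "will receive the I-HoME intervention (n=50) for up to six weeks".
- **Attrition.** A simulation modelled attrition directly, drawing on data from 1,000 home hospice patients, with mortality of "35% at four weeks, 62% at eight weeks, and 72% at twelve weeks". It also made an assumption about late data: "We assumed everyone would have at least 1 measurement after hospice discharge, including patients who died during week 1 of the intervention". Separately, 10% are expected not to complete post-test assessments.
- **Derived share.** "This means we would have 7 measurements on approximately 28% of the data".
- **Power over seven time points.** d = 0.8 is needed for 80% power. For d = 0.71 (a 25% reduction in burden): "We would have 70% power for a two-tailed hypothesis test across 7 time points".

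The Brief Description of Project Design in the data and safety monitoring plan describes allocation to I-HoME or "to standard home hospice care (n=50) for twelve weeks". It too lists measures only up to week 6.

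**The concern.** The sentence with the 28% is worded as a consequence of the mortality figures. For a schedule that ends at week 6, the relevant quantity is survival to week 6. The 28% instead matches survival to week 12, six weeks after the last scheduled measurement.

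Two things are at stake, both modest.

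- **The power results.** If the sentence is only misworded, the power figures are untouched. If the simulation placed its seven time points over twelve weeks, the d = 0.8 and 70% results belong to a different schedule from the one the trial will run. For example, measurements every two weeks from 0 to 12 also number seven, and completers would then be exactly 28%. That origin is conjecture, but it shows that a count of seven time points does not identify the schedule.
- **Feasibility.** Attrition is a feasibility measure, and 28% is the only expected complete-data share that the plan gives. Against a 28% benchmark, 40% completion would look better than planned. Against about 50% it would look worse.

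**Working it through.** **Inputs** (all from Brief overview of analytic methods): mortality 0.35, 0.62 and 0.72 at weeks 4, 8 and 12; seventh measurement at week 6; 10% non-response; d = 0.8 for 80% power and 70% power at d = 0.71 over seven time points; d = 0.57 for 80% power and 94% power at d = 0.71 with an early effect. Write S(t) for survival to week t.

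**1. Reproduce the plan's figure.** 1 − 0.72 = 0.28. This is S(12).

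**2. Bounds at week 6.** S(4) = 1 − 0.35 = 0.65 and S(8) = 1 − 0.62 = 0.38. Survival cannot rise, so 0.38 ≤ S(6) ≤ 0.65. The value 0.28 lies outside this range, and no interpolation is needed to show it.

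**3. Point estimates at week 6.**
- Linear: (0.65 + 0.38)/2 = 0.515.
- Log-linear (constant hazard between weeks 4 and 8): √(0.65 × 0.38) = 0.497.
- A monotone cubic through the points gives 0.495. Exponential and Weibull fits both give about 0.51.

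**4. Can anything in the plan bring this down to 28%?**

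| Adjustment | Share with all seven |
|---|---|
| 10% non-response at the lower bound | 0.38 × 0.90 = 0.342 |
| 10% non-response at the point estimates | 0.90 × 0.497 = 0.447 to 0.90 × 0.515 = 0.464 |
| Post-discharge measurement counted as the seventh when death falls between weeks 5 and 6, so S(5) applies | log-linear 0.65 × (0.38/0.65)^(1/4) = 0.568; linear 0.583 |
| Mortality counted from admission, enrolment at week 1, log-linear | S(7)/S(1) = 0.435/0.898 = 0.48 |

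None reaches 0.28. Getting there from S(6) would need a further loss of 1 − 0.28/0.38 = 26% to 1 − 0.28/0.65 = 57% of week-6 survivors (44% to 46% at the point estimates). The plan states no such loss.

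**5. Are the power figures consistent with each other?** With two-sided α = 0.05, SE = d₈₀/(1.960 + 0.842) and power = Φ(d/SE − 1.960).
- d₈₀ = 0.8: SE = 0.2856, and power at 0.71 is 0.701 (stated 70%).
- d₈₀ = 0.57: SE = 0.2035, and power at 0.71 is 0.937 (stated 94%).

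They are. This does not reveal which measurement times were simulated.

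**6. A crude look at scale.** This is a two-sample comparison using completers only, from 50 per arm; ranges cover the normal and t calculations.

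| Completers per arm | d for 80% power | Power at d = 0.71 |
|---|---|---|
| 14 (28% of 50) | 1.06–1.10 | 44–47% |
| 24.8–25.8 (49.7%–51.5% of 50) | 0.78–0.81 | 69–72% |

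The printed d = 0.8 and 70% sit near the second row. The planned mixed model also uses partial data, so this is not the planned analysis and does not establish what was simulated.

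**The case against.** The strongest reply accepts that 28% is the wrong figure but denies that it matters. The sentence summarises the mortality data, and nothing says 28% was fed into the simulation. The text just before the simulation sets out baseline plus weeks 1 to 6, so the natural reading is that this schedule was simulated. The power figures agree with one another, and none is shown to be wrong. The twelve-week wording in the monitoring plan is a separate inconsistency and says nothing about the simulation. The trial is also described, under Interim Analysis, as a feasibility and not an efficacy trial.

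Much of this stands. The 28% is a derived statement, and no power figure is shown to be in error. The completers-only check carries little weight: starting from 45 per arm (the 90 dyads left after 10% attrition), it gives d = 0.82–0.86 and 64–68% power, a looser match to the printed values.

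It is also fair that 38% to 65% bounds survival, not completion. Live discharge, withdrawal and missed surveys could lower the share, while bereaved caregivers who keep responding could raise it. The mortality clock (admission or enrolment) is not stated either. These points limit the precision of about 50%. They do not rescue 28%, which the plan derives from mortality alone.

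**Conclusion.** The concern holds as a minor error. The stated 28% is week-12 survival attached to a schedule that ends at week 6. On the plan's own mortality, week-6 survival is between 38% and 65%, about 50% by interpolation, and about 45% to 46% after a further 10% non-response.

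The bounds rest only on the printed mortality and on survival not increasing. The value of about 50% also assumes a smooth curve between weeks 4 and 8, and equating survival with complete data assumes no other loss.

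Whether d = 0.8 and 70% are affected cannot be settled from the documents, because the simulated measurement times, variance and correlation are not given. If twelve weeks was simulated, more complete data would be expected under the six-week schedule, so the stated power is probably conservative. Sample size and conduct are unaffected. Confidence is high for the mismatch itself; the effect on power remains an open question.

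**What to change.** 1. Replace 28% with the share expected to have all seven measurements at week 6, computed from the same 1,000-patient data. The interpolated 50% shows the likely size and should not be used as the replacement value. State whether time runs from admission or enrolment, whether the 10% non-response is included, and whether the post-discharge measurement can count as one of the seven.
2. State the measurement times used in the simulation. If they were baseline plus weeks 1 to 6, confirm d = 0.8 and 70%. If not, rerun on that schedule and restate both.
3. Reconcile the twelve-week duration in the Brief Description of Project Design with the six weeks in the Aim 3 and power sections.

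The cost is a text correction and at most one rerun of an existing simulation.

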**Aim 3:** For the pilot RCT, I will be collaborating with VNS Health home hospice teams (each team consists of 5-7 nurses). These two teams will be randomized to receive the intervention (I-HoME) or standard care at the nursing level. Since this is a pilot study and the primary aim is to assess for intervention feasibility, we acknowledge that we will not be able to control for certain differences. We will work with VNS Health hospice leadership to select hospice teams that serve similar patient populations. In both hospice teams, family CGs will be screened for study eligibility within 7 days of their home hospice admission through chart review. Screening will be conducted regularly by the research team. Prior to reaching out to potential participants, the

research team will contact the nurse caring for the patient and CG to confirm that it would be appropriate to contact the CG for the study. Weill Cornell and VNS Health are co-engaging one or more research staff through a subaward – they will be hired by VNS Health and performing the initial screening/recruitment. VNS Health staff will contact subjects by phone to inquire about their interest in participating (see telephone script C and D). If there is interest expressed by the CG over the phone, a research team member will reach out to conduct an in-home visit to describe the study and obtain written informed consent.

No external investigators (unless they are a VNSNY employee or VNSNY volunteer/intern) will be given names or contact information until subject approval is obtained through a VNSNY provider.

Hospice patients (n=20) will be referred by caregivers that are enrolled in the study. The study team will ask the caregiver (after they have been consented) if the patient would be open to participating in the study to provide ratings on their symptoms. Patients with a hospice diagnosis of dementia not be considered for the study. Eligible patients will be contacted by phone by a research team member.

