## Brief overview of analytic methods.

Feasibility will be assessed by examining accrual rates, attrition rates, adherence to the study protocol, hardware/software issues, and use of the intervention (e.g., frequency and duration of visits, number of educational video views). A feasibility questionnaire will be administered at the end of the intervention to CGs and to patients (if alive).

To measure potential efficacy, we will use mixed models (MMs) to analyze specific outcomes (i.e., symptoms, CG burden, hospitalization, etc.). MMs do not assume that each subject will contribute data at all-time points and so they can be used for data with complex attrition patterns. In these models, the subject's initial status (intercept) and the change in their status (slope) will be treated as random effects. The variables of group, time, the interaction of group and time, and any variable that differs between the two conditions at baseline or other variables of theoretical interest, expectation for inclusion in models from the literature, or near significance of difference by conditions will be modeled as fixed effects. Nurses will be examined in models as levels of a random classification factor. For all variables, four models will be tested: a linear effect of time, a log-linear effect of time allowing for more rapid change at the beginning of the study, a quadratic effect of time with no random slope for the quadratic term, and a quadratic effect of time with the slope of the quadratic term also being allowed to be random. Model selection will be done using the Bayesian Information Criterion, a measure of model misfit with a penalty added for extra parameters, with inferences only being made from the best fitting model. We will also test for a random intercept and random effect of time by hospice nurse to control potentially for nesting by nurse. Given the small number of hospice nurses we anticipate to be involved in the study, we do not expect either random effect to be statistically significant and plan to drop it from the model if it is not. We will also test for effects in CGs who are bereaved very early in the study.

Mixed model analysis will be conducted on seven outcomes.

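### Aim 3 randomises by nurse, but the nurse terms are dropped when non-significant, and the two-time-point power is not shown to hold for a nurse-randomised analysis

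*Combined protocol and SAP*

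**What the plan says.** **Allocation.** The section on the Aim 3 pilot RCT states: "The intervention will be randomized by nurse". The Aim 3 paragraph under the recruitment procedures describes "VNS Health home hospice teams (each team consists of 5-7 nurses") and adds: "These two teams will be randomized to receive the intervention (I-HoME) or standard care at the nursing level". Two teams of 5-7 give 10-14 nurses. The total is not stated anywhere. The project description in the Data and Safety Monitoring Plan differs: it assigns by hospice team.

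**Analysis.** The analytic methods section plans mixed models with group, time and their interaction, and random subject effects. It will also test a nurse random intercept and a nurse-by-time random effect. The reasoning begins "Given the small number of hospice nurses we anticipate to be involved in the study" and goes on to say that neither effect is expected to reach significance and that it will be removed if it does not.

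**Power.** The same section says: "With two time points for each subject we will have 80% power to detect an effect size of" d=0.57. For a 25% reduction in caregiver burden, equated to d=0.71, it says: "if the intervention is successful by week 1, we would have 94% power to detect an effect of this size". The figures come from a simulation built to model attrition, in which: "We assumed everyone would have at least 1 measurement after hospice discharge". No ICC, nurse count or correlation between baseline and later scores is given.

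**Status of efficacy.** The recruitment section says that "the primary aim is to assess for intervention feasibility".

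**The concern.** When whole nurses are allocated, caregivers who share a nurse may resemble one another, and the comparison has to allow for that. The plan allows for it only if a significance test says so. With 10-14 nurses, a non-significant result is likely even when real nurse variation exists. The small number of nurses, which the plan gives as its reason to expect to drop the terms, is therefore a reason not to rely on that test.

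Two things are at stake. First, the potential-efficacy tests may reject too often if nurse variation is present in what they compare and the term has been dropped. Second, the printed two-time-point power may describe an analysis of independent caregivers and not the nurse-randomised one. The first matters more, because it can still change reported results.

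**Working it through.** **Inputs from the documents:** 50 v 50 caregivers; two-sided test; two teams of 5-7 nurses, so k = 10 to 14; everyone has at least one later measurement, so N = 100 at two time points; printed power 80% at d=0.57 and 94% at d=0.71.

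**Assumptions (not in the documents):** alpha 0.05; ICC 0 to 0.10; baseline correlation r of 0 or 0.5; equal or near-equal numbers per nurse; k-2 degrees of freedom (df) for the nurse-level test, because the plan names no df method.

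**1. The printed power.** For independent caregivers the standard error of d is √(4/N) = √(4/100) = 0.20. The noncentrality is 0.57/0.20 = 2.85 and 0.71/0.20 = 3.55. With 98 df, the noncentral t gives 80.6% and 94.0%, and the effect detectable with 80% power is 0.566. These are the printed figures. The match is not unique: 45 v 45 with baseline as a covariate at r=0.3 gives 80.0% and 93.7%.

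**2. How often the nurse effect is detected.** Simulation with d=0, N=100, 40,000 runs per cell and an F-test for nurses within arm at 5%. The rule is a t-test on nurse means (k-2 df) if the F-test is significant, otherwise a caregiver-level t-test. The ICC here is in the score being compared.

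| ICC | Nurse effect detected, k=10 / 12 / 14 | Type I error of the rule, k=10 / 12 / 14 |
|---|---|---|
| 0.02 | 11.2 / 10.1 / 9.7% | 6.4 / 6.2 / 5.7% |
| 0.05 | 23.5 / 21.9 / 20.4% | 8.1 / 7.7 / 7.1% |
| 0.10 | 46.5 / 44.2 / 42.3% | 9.5 / 8.6 / 8.2% |

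Always using the nurse-level test holds about 5%.

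**3. Which kind of nurse variation matters.** The planned efficacy term is group by time. With two time points this is a comparison of change, and a nurse effect that is the same at both times cancels. Simulating that case (stable nurse intercept with ICC 0.05 and 0.10, r=0.5, nurse term dropped) gives a type I error of 4.8-5.1%. The 7-8% in step 2 therefore applies only if the 0.05 is nurse-level variation in change, or if post-scores are compared.

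**4. Illustrative nurse-level power at d=0.71, N=100.** Variance = (4/N) × [1 + (m-1) × ICC] × (1-r²), with m = N/k and df = k-2. This takes baseline as a covariate and applies the same ICC to the adjusted score.

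Example with ICC 0.05 and r=0:
- k=10: m=10, design effect 1 + 9 × 0.05 = 1.45, variance 0.04 × 1.45 = 0.058, noncentrality 0.71/0.241 = 2.95, 8 df, power 73.4%.
- k=14: m=7.14, design effect 1.307, noncentrality 0.71/0.229 = 3.10, 12 df, power 81.3%.

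| ICC | r=0, k=10 to 14 | r=0.5, k=10 to 14 |
|---|---|---|
| 0 | 87-90% | 95-96% |
| 0.02 | 82-87% | 91-94% |
| 0.05 | 73-81% | 85-91% |
| 0.10 | 62-73% | 74-84% |

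With r=0, the effect detectable with 80% power is 0.61-0.64 at ICC 0 and 0.70-0.77 at ICC 0.05, against the printed 0.57. If baseline enters as a repeated measurement, 1-r² is replaced by 2(1-r), so r=0.5 gives the r=0 column.

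**The case against.** **The power figures are not an arithmetic error.** This stands. They reproduce, and the documents do not say how the simulation treated nurses or baseline. A reader might infer that it ignored clustering and that 94% is wrong. The match with independent caregivers cannot show that, since other set-ups give the same figures. At ICC 0 the gap from 94.0% to 87-90% comes wholly from using 8-12 df in place of 98, a choice the plan neither makes nor rules out.

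**The inflated error belongs to a different test.** This stands in part. A reader might take 7-8% as the error rate of the planned group-by-time test whatever the source of nurse variation. It is not, because a stable nurse intercept cancels. Nurse-by-time variation does not cancel, the plan recognises it by proposing to test it, and the same rule would drop that term too. The documents give no value for it.

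**The choice of 100 dyads rests on another calculation:** 90 dyads and d=0.66. Independent 45 v 45 detects 0.597 with 80% power, so 0.66 carries (0.66/0.597)² = 1.22 times the variance. That could be an allowance for clustering (ICC 0.03-0.04 with 10-14 nurses), but the plan does not say so. It is one reason not to ask for a larger sample.

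**This is a feasibility pilot with data already in hand.** This stands as a limit on importance. The monitoring plan calls it a feasibility and not an efficacy trial, and the Aim 4 section refers to data already collected. Mixed models are still planned for seven outcomes, and the rule for the nurse terms governs their error rates.

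**Conclusion.** The concern holds in a limited form. Dropping the nurse terms on non-significance is unsafe with 10-14 nurses: at an assumed ICC of 0.05 the nurse effect is missed about 76-80% of the time. The type I error is then about 7-8% if that ICC is in the quantity tested, and about 5% if the nurse variation is only a stable intercept and the test is group by time.

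The two-time-point power is unsupported for a nurse-randomised analysis but not shown to be wrong. Depending on the unstated inputs, a nurse-level test at d=0.71 could have more than 94% power (95-96% at ICC 0, r=0.5) or clearly less (73-81% at ICC 0.05, r=0). No error is shown in the seven-time-point figures, which were not tested here.

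The consequence is minor: only the potential-efficacy tests are affected. The allocation unit also needs settling. If allocation were by team, with two teams, there would be one cluster per arm and no valid between-cluster test.

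**What to change.** 1. **Analysis section.** Keep the nurse random intercept and the nurse-by-time effect in the models whether or not they are significant, and name a small-sample df method. Settle this before the Aim 3 groups are compared. Cost: if the true ICC is 0, up to about 4-7 points of power at d=0.71 relative to a caregiver-level test (94.0% to 87-90%, N=100, r=0).
2. **Power section.** Keep N=100. Restate the two-time-point figures as a range over assumed ICC (for example 0 to 0.10), nurse count (10-14) and baseline correlation, and say whether baseline is a covariate or a repeated measurement. Use assumed values, not observed Aim 3 results. Cost: a short recalculation, and power that may read less favourably.
3. **Allocation unit.** Reconcile the monitoring plan's project description (by hospice team) with the Aim 3 and recruitment sections (by nurse), and state the number of nurses. Cost: a text edit.

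None of these needs extra participants or visits.
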